The Therapeutic Effects of Forced Aerobic Exercise in Multiple Sclerosis

Statistical Analysis

NCT Number: 04906057

Document Date: 07/15/2021

Section of Biostatistics
Quantitative Health Sciences/ JJN-3
[name]

IRB 19-1003: Feasibility study investigating forced and voluntary rate aerobic cycling in persons with multiple sclerosis

Statistical Methods:

Demographics, patient characteristics and exercise parameters will be summarized by mean with standard deviation or median with interquartile range for continuous variables, and count with percentage for categorical variables. Patients will be stratified by exercise groups (FE vs VE).

Changes in motor and non-motor functions from baseline to end of treatment will be examined by paired sample t-tests.

Changes in Klotho level from pre- to post-exercise will be examined by paired sample t-tests, at both first exercise session and last exercise session. Changes in Klotho level from first exercise session to last exercise session will also be examined by paired sample t-tests, at both pre-exercise and post-exercise. Mixed-effect model will be used to examine if there is significant acute change (from pre- to post-exercise) or long-term change (from first to last exercise session) in Klotho level. Patient random effect and exercise group indicator (FE vs VE) will be included in the model. Changes in Neurofilament light (NFL) from baseline to end of treatment will be examined by paired sample t-test.

Effects of exercise parameters on walking outcomes at end of treatment will be examined by linear regressions. Exercise parameters will be in separate models and baseline values of walking outcomes will be adjusted for in the models.

Outcomes measured at end of treatment will be compared between groups using linear regressions. Baseline values of outcomes will be adjusted for in the models.

Changes in exercise parameters over sessions will be examined by mixed-effect models, where session is the independent variable. Patient random effect will be included in the model. Group difference in changes in exercise cadence over sessions will be examined by mixed-effect models, where independent variables include session, group and interaction between session and group. Patient random effect will be included in the model.

We will also compare variables (motor and non-motor functions) between baseline1 and baseline2 using paired sample t-tests.

P<0.05 will be considered as statistically significant.

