### **Data Variables**

**Exercise Training Variables:** Overall time, active exercise time, heart rate, cadence, and power are recorded in a secure, customized REDCap database. The primary training variables of interest for each exercise session are: AE intensity measured as percent heart rate reserve (%HRR) during main 35-minute exercise set, average cadence and work (power) produced by the patient and for the FE participants, by the motor.

**Measures of Feasibility (Aim 1):** Primary outcomes to determine feasibility will include measures of exercise compliance (percent of sessions attended, time spent exercising, time spent within target heart rate zone) and the absence of adverse events. Secondary outcomes will include change in levels fatigue and physical activity as measured by a body-worn activity monitor.

**Effects on Motor Function (Aim 2):** The primary outcome is change in biomechanical characteristics of gait, while the secondary outcomes include changes in walking capacity, manual dexterity test (MDT), and timed up and go (iTUG).

**Effects on Non-Motor Function (Aim 3):** The primary outcome measuring QOL is the change in the PROMIS-29, while the MSPT CVLT, and BVMT will serve as the primary outcomes measuring cognitive function.

**Role of Klotho (Aim 4):** The primary outcome is the acute and long-term change in serum Klotho levels from baseline to the post-exercise intervention, while the secondary outcome in long-term change in sNfL

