### **Outcomes:**

**Analysis of Feasibility (Aim 1):** Measures of compliance will determine feasibility of individuals with MS to complete the FE intervention. Self-reported fatigue will be measured using the Modified Fatigue Impact Scale. Activity levels will be measured using a Garmin Vivofit 4 body-worn activity monitor. The absence of adverse events will demonstrate safety of FE in MS.

**Biomechanical Gait Assessment (Aim 2):** The CAREN system is a complete biomechanical assessment system with 10 Vicon cameras, split-belt treadmill with two force plates, and D-flow software. Twenty-five retro-reflective markers will be placed at anatomic landmarks identified for LE assessment. Participants will walk at a self-selected pace for two 2-minute trials. The following biomechanical outcomes will be calculated: 1) spatio-temporal: velocity; cadence, step length, percentage of gait cycle spent in swing and stance phase, single and double limb support time and percentage; 2) Kinematic: hip and knee flexion and extension; ankle dorsi- and plantar-flexion; pelvic obliquity, rotation and tilt. To determine changes in overground walking, gait analysis will also be conducted using the Zeno Instrumented walkway. Participants will walk at a self-selected pace and fast pace for four lengths for each condition along the 15' Zeno Instrumented walkway. The following spatio-temporal outcomes will be calculated: velocity; cadence, step length, percentage of gait cycle spent in swing and stance phase, single and double limb support time and percentage. Lastly, the Timed up and Go will be administered.

**Non-Motor Function Data (Aim 3):** The PROMIS-29 will be administered to determine self-reported quality of life. The multiple sclerosis performance test (MSPT) and two measures of episodic memory, the California Verbal Learning Test and the Brief Visuospatial Memory Test, will be administered to examine change in cognitive function. All will be administered to determine feasibility with respect to administration approach, sensitivity to detect change over time, and time requirements for a future clinical trial.

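### The regressions of walking outcomes on exercise parameters are judged slope by slope at P<0.05, with neither set listed, no multiplicity control and no exploratory label

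*SAP*

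**What the plan says.** The SAP, under Statistical Methods, states: "Effects of exercise parameters on walking outcomes at end of treatment will be examined by linear regressions". The next sentence sets the structure: "Exercise parameters will be in separate models and baseline values of walking outcomes will be adjusted for in the models". The SAP closes with a single rule for all its analyses: "P<0.05 will be considered as statistically significant". It does not list the parameters or the outcomes, and it gives no hierarchy, no adjustment and no exploratory label for this set of models.

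The protocol does not narrow the family.

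- **Exercise parameters.** Data Variables names as the main training variables "AE intensity measured as percent heart rate reserve (%HRR) during main 35-minute exercise set, average cadence and work (power) produced by the patient", with motor work added for the FE group only. It also says: "Overall time, active exercise time, heart rate, cadence, and power are recorded in a secure, customized REDCap database".
- **Walking outcomes.** Under Outcomes, the gait assessment yields "velocity; cadence, step length, percentage of gait cycle spent in swing and stance phase, single and double limb support time and percentage", first on the treadmill and again on the instrumented walkway, where "Participants will walk at a self-selected pace and fast pace for four lengths for each condition". Kinematic variables and the Timed Up and Go are further measures. The primary outcome of Aim 2 is gait biomechanics as a domain, not one variable.
- **Hypotheses and labels.** None of Hypotheses 1 to 4 ties a particular training variable to a particular walking measure. Only Aim 4 (Klotho) is called exploratory.

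**The concern.** One parameter per model, several parameters and several outcomes make a grid of tests, each at the full 5% level. If no training variable influences walking, the chance that some slope falls below P<0.05 rises with the size of that grid, and the SAP's wording would allow that slope to be reported as a significant effect of an exercise parameter. Because neither set is listed, the grid could also be settled after the results are known.

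This family is separate from the before-after tests and the between-group comparisons. Naming one lead gait measure for those would not settle it, since at least three parameters would still each be tested against that measure.

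At stake is what a reader may conclude about intensity, cadence or work as the component of training related to walking.

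**Working it through.** The documents give no number of tests and no family-wise error rate, so there is no figure of theirs to reproduce.

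**Inputs from the documents**
- Threshold 0.05 per test (SAP); taken as two-sided, since sidedness is not stated.
- n = 20 randomised (protocol, Experimental Overview); 24 recruited (Recruitment and Sample) used as a check.
- Three parameters available in both groups: %HRR, cadence, patient work (Data Variables). Motor work is left out because it exists only in FE.
- Nine spatio-temporal measures per walking condition: velocity, cadence, step length, swing %, stance %, and time and percentage for each of single and double limb support. Three conditions (treadmill, walkway self-selected, walkway fast) plus Timed Up and Go give 3 x 9 + 1 = 28.

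**Assumptions**
- The number of walking outcomes K: 1, 2, 4, 10 or 28. The value 4 could be three velocities plus Timed Up and Go; 10 could be one condition's nine measures plus Timed Up and Go.
- A common correlation among parameters and among outcomes: 0.2, 0.5 or 0.8.
- Baseline-to-end correlation 0.7. A run with 0.8 gave closely similar results.

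**Method**
1. Number of tests m = 3K. Expected false positives = 0.05m.
2. If the tests were independent, the chance of at least one is 1 - 0.95^m.
3. For correlated tests, data were simulated with no true parameter effect. The end value was regressed on one parameter and the baseline value for every pair (t test on n - 3 = 17 df), and the share of replicates with any P<0.05 was counted. The error of a single test stayed at about 0.05, so the excess comes from the number of tests and not from the model.

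**Results, n = 20**

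| Grid | m | Expected false positives | Independent | Corr. 0.2 | Corr. 0.5 | Corr. 0.8 |
|---|---|---|---|---|---|---|
| 3 x 1 | 3 | 0.15 | 14% | 14% | 13% | 10% |
| 3 x 2 | 6 | 0.30 | 27% | 25% | 23% | 16% |
| 3 x 4 | 12 | 0.60 | 46% | 44% | 36% | 23% |
| 3 x 10 | 30 | 1.5 | 79% | 75% | 60% | 34% |
| 3 x 28 | 84 | 4.2 | 99% | 97% | 87% | 47% |

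Repeat runs differ by up to about 3 percentage points. With n = 24 the 12-test figure at correlation 0.5 is again 36%, so the gap between 20 and 24 does not matter here.

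Relative to 5%, the inflation runs from 10/5 = 2 times (3 tests, correlation 0.8) to 97/5 = about 19 times (84 tests, correlation 0.2).

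**The case against.** The strongest reply is that the family is the reader's construction. The SAP uses two plurals without a list, and does not say that every parameter is crossed with every outcome. The protocol separates gait biomechanics, walking capacity and the Timed Up and Go, so the walking outcomes could be a short list. The 84-test grid also contains near-duplicates, such as swing and stance percentages of the same gait cycle. This stands: the family size has to be shown as a range, and the low end is modest.

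A second reply is that this is a pilot, called a feasibility study in the SAP's own heading, and that no stated hypothesis rests on these slopes. This lowers the weight of the point but does not remove it. The protocol also seeks initial efficacy, it reserves the exploratory label for Aim 4, and the SAP attaches a significance rule to results that it calls effects.

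A reader might infer more than the documents support:

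- **That a false finding is more likely than not.** With 12 tests or fewer the chance stays below one half even if all tests are independent (46%).
- **That inflation is at least fourfold in every case.** With 3 tests it is 2 to 3 times.
- **That these slopes will select the training component for a later trial.** Neither document says so.
- **That the large slope needed for significance at n = 20 shows a multiplicity problem.** The partial correlation must reach 2.110/sqrt(17 + 2.110^2) = 0.46, but that holds for any single test of this size.
- **That one lead pair should be named and tested.** Exercise parameters arise after randomisation and depend partly on arm: FE has a target of 80 RPM, VE a self-selected cadence, both share a heart-rate zone, and the SAP describes no group term in these models. A lead pair would lend confirmatory standing to an observational slope.

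**Conclusion.** The point holds in a limited form. The SAP applies an unadjusted P<0.05 to an unlisted family of baseline-adjusted slopes and calls them effects. If no parameter affects walking, the chance of at least one false claim is above the nominal 5% for any grid with more than one test. It is roughly 10-14% if a single walking outcome is meant, 16-25% for two, 23-44% for four, and 47-97% for the fullest grid considered. It exceeds one half only for the larger grids (30 or 84 tests in the table) at low to moderate correlation.

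These sizes rest on three parameters, an assumed number of outcomes, equal correlations of 0.2 to 0.8 and a two-sided test. The number of outcomes and the correlations drive the range; n = 20 or 24 makes no material difference. The defect lies in what may be concluded, not in the regression model or the data collected, and the pilot setting makes it an inexpensive correction rather than a threat to the study.

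**What to change.** In the SAP's Statistical Methods, amend the paragraph on exercise parameters and walking outcomes to state that:

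1. the P<0.05 rule does not apply to these regressions;
2. all parameter-by-outcome slopes are exploratory and are described as associations, not effects;
3. each slope is reported with its 95% confidence interval, together with the total number of models fitted.

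If the sponsor wishes to keep P values for declaring significance, replace item 1 with a false-discovery-rate procedure across the whole family. The parameters and outcomes in that family then have to be listed before analysis, because the procedure depends on their number.

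The cost is a few sentences of SAP text, with no new data, visits or participants. The downside is that no single slope can be declared significant without adjustment, which suits a pilot.

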### **Approach**

**The aim of this project is to conduct a pilot study to investigate the feasibility and initial efficacy of applying FE to individuals with MS to improve motor function, cognitive function, and QOL.**

**Experimental Overview:** A pilot study is proposed in which 20 individuals with MS presenting with an Expanded Disability Status Scale score between 2.0 and 6.5 will be eligible to participate. Participants will be screened using the American College of Sports Medicine Exercise Preparticipation Health Screening algorithm. The potential participant's physician will be notified of the study protocol and their patient's desire to participate. Eligible participants will undergo clinical and biomechanical assessments evaluating lower extremity function, processing speed, memory, and self-reported quality of life at baseline and post-intervention. Following baseline testing, participants will be randomized to undergo FE (n=10) or VE (n=10). Randomization will be stratified based on EDSS level (2.0-4.0 vs. 4.5-6.5) to facilitate comparable levels of disability in both groups. Participants in both groups will attend exercise sessions twice a week for 12 weeks. The FE intervention will consist of forced-rate aerobic exercise on a stationary semi-recumbent bicycle. Target cadence will be 80 revolutions per minute (RPM). Should the participant not tolerate the 80 RPM cadence, a self-selected cadence will be used initially, and increased by 5 RPM each session until the target cadence of 80 RPM is achieved. The VE intervention will be identical to FE, except participants will cycle at a self-selected cadence on a semi-recumbent stationary cycle ergometer without assistance from the motor. Aerobic intensity for both groups will be monitored continuously throughout the exercise using a heart rate chest strap. Target heart rate will be prescribed at 60-80% of the individual's age-predicted maximum. Following a 5-minute

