warm-up, participants will complete a 35-minute main exercise set with the goal of maintaining their heart rate within the prescribed target zone. A 5-minute cool-down will occur immediately at the end of the 35-minute main exercise set. For the FE group, the cadence during warm up and cool down will be 15-20% less than the target cadence for the main exercise set (80 RPM) during the main exercise set. Water will be provided to the participant ad libitum, but all will be encouraged to drink 16-24 ounces during the exercise session. Cooling vests will be available to participants to avoid overheating as indicated. Rest breaks will be provided as requested, but all participants will be encouraged to progress to an entire 45-minute session without rest breaks.

**Recruitment and Sample:** Physicians and advance practice clinicians within the Mellen Center who would otherwise prescribe physical therapy to their patients will provide prospective participants with a study brochure. Should they express interest in learning more about the study, the study coordinator will call them to follow up. The study team may use MyChart as a way to contact eligible patients with an IRB approved flyer and/or brochure. Twenty-four patients will be recruited for this pilot feasibility study.

**Aim 1: To determine the feasibility of applying FE or VE training to individuals with MS.** Primary outcomes to determine feasibility will include measures of exercise compliance (percent of sessions attended, time spent exercising, time spent within target heart rate zone) and the absence of adverse events. The secondary outcomes will include change in levels fatigue and physical activity.

**Hypothesis 1:** Participants will comply with the FE or VE intervention (exercise frequency, time, and intensity) at  $\geq 90\%$  of the prescribed values and will present with no worsening fatigue or levels of sedentary activity following the FE or VE intervention.

**Aim 2: To determine the effects of a 12-week FE or VE intervention on motor function.** The primary outcome is change in biomechanical characteristics of gait. Secondary outcomes include changes in walking capacity, balance, manual dexterity test (MDT), and timed up and go (iTUG).

**Hypothesis 2:** Improvements in gait biomechanics and walking capacity will be observed following the 12-week FE intervention.

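### Randomisation is stratified by EDSS level, but the FE-VE regressions adjust only for the outcome's own baseline, so precision may be lost if EDSS is prognostic beyond that baseline

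*SAP*

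**What the plan says.** The protocol (Approach, Experimental Overview) makes EDSS level the stratification factor: "Randomization will be stratified based on EDSS level (2.0-4.0 vs. 4.5-6.5) to facilitate comparable levels of disability in both groups". It plans 10 participants per arm. Recruitment and Sample gives a different total: "Twenty-four patients will be recruited for this pilot feasibility study".

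The SAP (Statistical Methods) describes the arm comparison in two sentences: "Outcomes measured at end of treatment will be compared between groups using linear regressions. Baseline values of outcomes will be adjusted for" in the models. EDSS does not appear in the SAP, and no reason is given for leaving it out. The SAP's one use of the word stratified refers to summaries by exercise group.

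For exercise parameters the SAP says: "Effects of exercise parameters on walking outcomes at end of treatment will be examined by linear regressions". It continues: "Exercise parameters will be in separate models and baseline values of walking outcomes will be adjusted for in the models". No group term is named. The Experimental Overview sets a target of 80 RPM for FE, with an exception: "Should the participant not tolerate the 80 RPM cadence, a self-selected cadence will be used initially". VE cadence is self-selected throughout.

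**The concern.** Stratification balances a factor between arms, but the model's standard error reflects that balance only if the factor is in the model. If it is left out and is prognostic, its variance is counted as noise. The standard error is then too large, the test rejects less often than its nominal rate, and confidence intervals over-cover. There is no bias and no excess of false positives. With about 10 participants per arm, precision is scarce, and EDSS is already recorded because it decides eligibility and stratum.

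The secondary issue concerns cadence. Because arm strongly influences cadence, a slope fitted across both arms can pick up an arm difference that does not act through cadence, such as one due to motor assistance. It could then be read as dose-response.

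**Working it through.** Neither document gives a power calculation, effect size, SD or interval width, so there is no planned figure to reproduce. Three inputs come from the documents: two EDSS strata, N=20 (or 24), and a 0.05 significance level, taken as two-sided. Everything else below is assumed.

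**1. Formula.** Let R² be the share of outcome variance left after baseline adjustment that the stratum explains. With balanced arms,

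width ratio (with stratum / planned) = [t(0.975, N−4) / t(0.975, N−3)] × √(1 − R²).

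At N=20 the t-values are 2.120 (16 df) and 2.110 (17 df). For R²=0.20 the ratio is (2.1199/2.1098) × √0.80 = 0.899.

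| R² | N=20 | N=24 |
|---|---|---|
| 0 | 1.005 | 1.003 |
| 0.05 | 0.979 | 0.978 |
| 0.10 | 0.953 | 0.952 |
| 0.20 | 0.899 | 0.897 |
| 0.30 | 0.841 | 0.839 |

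Break-even at N=20 is R² = 1 − (2.1098/2.1199)² ≈ 0.01.

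**2. Simulation at N=20.** There were 20,000 trials per setting. Outcome was regressed on arm and baseline, with and without the stratum. Baseline-EDSS correlation was 0 or 0.5, and the strata were 5 per arm, 7/3 per arm, or uneven (8/2 vs 7/3).

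| Residual share explained | Change in 95% CI width | Type I error, planned test |
|---|---|---|
| 0% | 0.6-1.8% wider | about 5% |
| 10% | 4-5% narrower | 3.7-4.4% |
| 20% | 10-11% narrower | 3.1-3.5% |
| 30% | 16-17% narrower | 2.1-3.5% |

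Break-even rises to about 1-3.5% of residual variance, because chance imbalance and correlation with baseline add a little to the cost.

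Power was computed with 5 per cell for an arm difference of 1.2 SD, where SD is the residual SD after baseline adjustment. It goes from about 70% as planned to 73%, 78% or 83% at residual shares of 10%, 20% or 30%. It falls by up to 1 point if the stratum explains nothing.

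At N=24 (6 per cell) the intervals are 5%, 10-11% and 17% narrower, or 0.4-1.0% wider if the stratum explains nothing. The choice between 20 and 24 does not matter here.

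**3. Cadence.** Assume FE mean 80 (SD 3) and VE mean 60 (SD 10) RPM, N=20, and no true cadence effect. The average sample correlation of cadence with arm is 0.82. The pooled slope is significant in 5%, 13%, 25% or 47% of trials for arm effects of 0, 0.5, 0.8 or 1.2 SD. Three other assumed spreads (correlation 0.57-0.69) give 9-11%, 14-19% and 25-35% for the three non-zero arm effects. With group in the model, rejection returns to about 5%.

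Adding group has a price. At correlation 0.82 the standard error inflates by about 1/√(1 − 0.82²) = 1.75. This agrees with the simulated interval, which is 70-79% wider (13-42% under the other spreads). Power for a true slope worth 0.8 SD across the arm gap falls from 52% to 21%.

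**The case against.** The strongest reply is that the planned analysis is valid and the gain is hypothetical. Nothing in the documents shows that a two-level EDSS split explains 10-30% of what baseline leaves over. For outcomes such as gait velocity, the baseline value may already carry most of the EDSS information. At a 5% share the interval narrows by only about 2%, and at zero it widens slightly. The protocol's stated purpose for stratifying is balance. Hypotheses 1-3 concern compliance and improvement after exercise, and the SAP examines those changes in function with paired t-tests, which this point does not touch. The SAP also names no confidence intervals, only P<0.05.

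Most of this stands as a limit on size. The intervals discussed are those the regressions imply, and the P values are conservative in the same way. It does not remove the point: the SAP plans FE-VE comparisons, the protocol aims at initial efficacy and looks to a future trial, and the downside of adjustment is under 2% of width.

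On cadence, every VE value is assumed, and the 47% comes from the most extreme spread with the largest arm effect. If the FE benefit acts through cadence, adding group removes real signal. That is a good reason not to replace the pooled model. Intensity could also track arm, since Hypothesis 4 expects FE to reach a higher level, but heart rate reserve and power were not simulated.

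**Conclusion.** The concern holds. The stratification factor is missing from the FE-VE regressions without explanation, and the consequence is possible loss of precision in the conservative direction. The size depends on an R² that the documents do not give: intervals 4-5% to 16-17% wider-than-needed territory is reached only if EDSS explains 10-30% of residual variance, the effect is about 2% at a 5% share, and there is no gain below roughly 1-3.5%. Because the possible gain is much larger than the possible loss, the change should be made. It is not a condition for the analysis to be valid. Confidence is medium, since the prognostic strength is assumed. The cadence point is secondary: it requires an arm effect that does not act through cadence, and the case for adding the stratum does not depend on it.

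**What to change.** Add the EDSS randomisation stratum as a covariate in each between-group end-of-treatment regression, or state why it is omitted. This takes a sentence in the SAP and one degree of freedom per model, with no new data.

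The stratum is not needed in the Klotho or session mixed models. The acute, long-term and over-session changes tested there are within-patient, although the group indicator in the Klotho model is itself a between-patient term.

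Keep the planned exercise-parameter regressions, but report them as exploratory associations and not as effects. For cadence, show a model with group added, or within-arm estimates, beside the pooled one. State that the adjusted interval is much wider: about 70-86% under the first assumed spread, where the upper end is the model that also includes the stratum. This adds one cadence model per walking outcome. No change is proposed for the other exercise parameters.

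### Both models over sessions name only a patient random effect; if patients' trends differ, the session and session-by-group tests use standard errors that are too small

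*SAP*

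**What the plan says.** The SAP, Statistical Methods, plans two models over sessions. The first is general: "Changes in exercise parameters over sessions will be examined by mixed-effect models, where session is the independent variable". The second is for cadence: "Group difference in changes in exercise cadence over sessions will be examined by mixed-effect models", with session, group and their interaction as fixed effects. For each, the random part is one sentence: "Patient random effect will be included in the model". Neither document names a random slope, a residual correlation structure, a robust standard error or a small-sample degrees-of-freedom method. The SAP closes by setting 0.05 as the significance level.

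The protocol's Approach section gives the number of sessions: "Participants in both groups will attend exercise sessions twice a week for 12 weeks". It also describes how cadence and exercise time may develop:

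- An FE participant who cannot tolerate the target cadence follows a ramp: "a self-selected cadence will be used initially, and increased by 5 RPM each session until the target cadence of 80 RPM is achieved". The others start at 80 RPM.
- In VE, "participants will cycle at a self-selected cadence on a semi-recumbent stationary cycle ergometer without assistance from the motor".
- Rest breaks are allowed, but "all participants will be encouraged to progress to an entire 45-minute session without rest breaks".

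The Data Variables section lists what is captured: "Overall time, active exercise time, heart rate, cadence, and power are recorded in a secure, customized REDCap database".

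**The concern.** A random intercept absorbs differences between patients in level, not in trend. If patients change at different rates, each patient's 24 values share a deviation from the arm's mean trend. A random-intercept model puts that deviation into the residual and treats it as independent noise. The test of session or session-by-group then behaves as if it had several hundred independent pieces of information, when the evidence on trends comes from about 20 patients.

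The FE ramp gives a documented reason to expect this in the cadence model. Patients who ramp and patients who start at target have different slopes by design. A training trend, or an FE-VE difference in cadence progression, could be declared significant more often than 5% of the time when there is none on average. FE is defined by its augmented cadence, so a significant difference in cadence progression is a result likely to be reported and carried into the future trial that the protocol mentions.

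**Working it through.** The documents contain no power or variance calculation, so there is no figure of theirs to reproduce.

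**Inputs from the documents.** Sessions per patient: 2 × 12 = 24. Patients: 10 FE and 10 VE (Approach). Alpha 0.05, taken as two-sided.

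**Assumptions.** All 24 sessions attended; independent residuals with SD σ; between-patient SD of the total change over the 23 steps equal to *r*σ. The documents give no value for *r*, so a range is used.

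**Closed form, session-by-group.**

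- Sum of squares of session number: 24 × (24² − 1)/12 = 1150.
- True variance of one patient's fitted slope, relative to σ²/1150: 1 + 1150*r*²/23² = 1 + 2.174*r*².
- Residual degrees of freedom under a random intercept: 480 − 20 − 2 = 458. Slope differences between patients within arms carry 18 df, so the expected residual variance is σ²(1 + 18 × 2.174*r*²/458) = σ²(1 + 0.0854*r*²).
- True SE / model SE = √[(1 + 2.174*r*²)/(1 + 0.0854*r*²)]. At *r* = 1 this is √(3.174/1.0854) = 1.71.

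| *r* | True SE / model SE | Type I error, closed form | Simulated, slopes vary in both arms | Simulated, slopes vary in FE only |
|---|---|---|---|---|
| 0 | 1.00 | 5.0% | 5.0% | – |
| 0.25 | 1.06 | 6.5% | 6.8% | 5.8% |
| 0.5 | 1.23 | 11.0% | 11.1% | 7.8% |
| 1 | 1.71 | 25.1% | 24.6% | 16.4% |
| 2 | 2.69 | 46.5% | 46.4% | 35.6% |

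The simulations used 20,000 replicates. The test of session alone, with slopes varying in both arms, gives 5.0%, 6.3%, 10.7%, 25.2% and 46.6%. A Welch t-test on per-patient slopes stays at 4.6% to 5.1%. A separate simulation of 8,000 replicates agrees. It also shows that 24 patients, the recruitment figure elsewhere in Approach, do not cure the problem: 11.2%, 24.9% and 46.5% at *r* = 0.5, 1 and 2.

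**The FE ramp.** The straight-line slope over 24 sessions for a patient who rises 5 RPM per session to 80 follows from the shortfalls below 80. From a start of 60 it is (11.5×20 + 10.5×15 + 9.5×10 + 8.5×5)/1150 = 525/1150 = 0.457 RPM per session. From 65 it is 0.283 and from 70 it is 0.146. A patient starting at 80 has slope 0.

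To isolate type I error, suppose each FE patient has a 50% chance of ramping, and VE is given the same mean slope so that the null holds. The residual SD is assumed.

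| Residual SD (RPM) | Start 70 | Start 65 | Start 60 |
|---|---|---|---|
| 10 | 5.3% | 5.8% | 7.5% |
| 5 | 5.8% | 8.9% | 14.4% |
| 2.5 | 8.3% | 16.3% | 26.6% |

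Per-patient slopes give 4.9% to 5.7% in these settings. With a 25% or 75% chance of ramping and starts of 60 or 50, they reach 7.2% to 7.8% at worst.

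**Klotho (secondary point).** The exploratory Klotho mixed model uses one patient effect for two kinds of change. With n = 20 and a variance ratio of 1 (assumed), the long-term/acute type I errors are 15%/1.2% if the day level varies between patients, and 1.4%/14% if the acute response varies. Per-patient changes hold 4.8% to 5.2%.

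**The case against.** The strongest case on the other side has four parts.

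- **Wording.** The SAP never says random intercept, and a patient random effect does not strictly exclude a slope. That is true. But no slope is named, the singular term is ordinarily read as an intercept, and the same one-sentence edit settles the matter either way.
- **Evidence that trends differ.** Self-selected VE cadence shows different levels, which an intercept absorbs, and does not itself show different trends. Rest breaks bear on active exercise time, which is recorded but is not among the primary training variables, and they do not bear on the cadence model. Both arms share a heart-rate target. This largely stands: the FE ramp is the one firm source. It is conditional, confined to one arm and over after a few sessions, so the figures with slopes varying in both arms rest on assumption. Even so, patients who reach one common cadence from different starting points must have different trends, and cadence is the parameter given the interaction test.
- **The null is artificial.** If some FE patients ramp and VE stays flat, FE truly rises on average and rejection is correct. This stands: a significant result produced by the ramp is not in itself a false positive.
- **Loss of power.** With half of FE ramping from 60, VE flat and residual SD 5 RPM, rejection falls from 0.90 with a random intercept to 0.58 with per-patient slopes. The team should know this. The comparison is not like for like, because part of the 0.90 comes from standard errors that are too small.

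**Conclusion.** The concern holds in its conditional form. Read in the ordinary way, the SAP's models give valid tests of session and session-by-group only if patients within an arm share one trend and residuals are independent. If trends differ, the standard errors are too small by a factor that grows with the spread: 1.23 at half a residual SD and 1.71 at one. Whether this is negligible or material cannot be settled from the documents, which give no slope variance, no residual variance and no number of patients who will ramp. In the ramp scenarios above, the error runs from about 5% to 27%.

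The reach is limited. These are secondary analyses of training parameters in a pilot, and none of the four hypotheses rests on a trend over sessions. The Aim 1 compliance outcomes, the end-of-treatment regressions and the paired t-tests, including those for Klotho, are unaffected. The change should be made because it is cheap and the SAP attaches a significance threshold to these tests. Confidence is medium, because the size rests on assumed variances.

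**What to change.** In both models over sessions, specify a patient random intercept and a patient random slope for session, with Satterthwaite or Kenward-Roger degrees of freedom. State in advance that, if the model does not converge, per-patient slopes will be compared by t-test. Plot cadence by patient as well, because a straight line only summarises a ramp that ends after a few sessions. For Klotho, base the acute and long-term conclusions on per-patient changes, as the planned paired t-tests already do.

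The cost is one sentence of SAP text and one model term. Non-convergence is possible with about 20 patients. If trends are in fact equal, intervals are about 7% wider (critical t of 2.10 on 18 df against 1.97 on 458 df; 2.10/1.97 = 1.07). Per-patient slopes are not perfect: their error reached 7% to 8% when a steep ramp occurred in only a few, or in most, FE patients.
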